**Attachment 9: New Concomitant Medications – Increase in dosage Calculation**

In case a participant receives the same medication with the same form at baseline and during an ARI episode, then in order to identify whether there was an increase in dose between baseline and ARI episode the medication dose will be calculated by multiplying the dosage per administration with the number of administrations per day or per week, as applicable for both timepoints and compared.

This rule applies for the following medication frequencies:

- Once weekly (1 time per week)
- Twice weekly (2 times per week)
- Three Times weekly (3 times per week)
- Four Times weekly (4 times per week)
- Twice Daily (BID)
- Twice per Month (BIM)
- Every two weeks (Every 2 weeks)
- Every four weeks (Every 4 weeks)
- Weekly (Every week)
- Once
- Per Year
- Every three months (Q3M)
- Daily (QD)
- Four times daily (Q1D)
- Monthly (QM)
- Every Other Day (QOD)
- Three times daily (TID)

For frequencies equal to ‘other’ at baseline, any change to one of the above frequencies will be considered an increase, given that the form remains the same.

For frequencies equal to ‘as necessary’ (PNR) or ‘occasional’, any change to another frequency or dose will be considered as an increase.

A change from ‘as necessary’ (PNR) to ‘occasional’ or ‘other’ will not be considered as an increase.

Moreover, capsule and tablet are considered the same form so to define if there was an increase the dose and the frequency will be used as defined above. The same applies for inhalant and aerosol.

For example:

Standardized Medication Name	Dose per Administration	Dose Units	Dose Form	Dosing Frequency per Administration Interval	Route of Administration	Timepoint
corticosteroids	50.0000	ug	AEROSOL	1 TIME PER WEEK	NASAL	Baseline
corticosteroids	50.0000	ug	AEROSOL	QD	NASAL	During ARI

Baseline dose is  $50 \times 1 = 50$  ug per week

During the ARI  $50 \times 7 = 350$  ug per week

This is considered an increase in dose for this medication.

Standardized Medication Name	Dose per Administration	Dose Units	Dose Form	Dosing Frequency per Interval	Route of Administration	Timepoint
GUAIFENESIN	600.0000	mg	TABLET	PRN	ORAL	Baseline
GUAIFENESIN	1200.0000	mg	TABLET	ONCE	ORAL	During ARI

This is considered an increase in dose for this medication since the frequency goes from as necessary to once.

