#### **4.10. Therapeutic Interventions**

The following are considered as therapeutic interventions of interest:

- New/increased bronchodilator/nebulizer treatment
- New/increased corticosteroid prescription
- New/increased antibiotic prescription
- New/increased antiviral prescription

These will be taken from the concomitant medication pages of the eCRF based on [Attachment 5](#).

The ones linked to an ARI or complication of an ARI will be displayed.

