##### **4.10.1. Analysis Methods**

The PPE set will be used to analyze the use of therapeutic interventions.

Therapeutic interventions taken at baseline will be summarized for all subjects in the PPE set.

Moreover, the proportion of participants with any RT-PCR confirmed RSV disease utilizing new therapeutic interventions and those with RT-PCR-confirmed RSV-mediated LRTD based on the 3 case definitions utilizing new therapeutic interventions will be tabulated per group and the corresponding VE (1-relative risk) with an exact Poisson 95% 2-sided CI will be determined and graphically depicted with a forest plot, similar to the primary analysis.

Baseline and new interventions are defined as in Section [4.1.4](#).

Depending on their occurrence, the above might be repeated for the different subcategories of therapeutic interventions or for subgroups (with or without calculation of VE).

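### Attachment 9's rule for a PRN or 'occasional' baseline ignores direction, so a lower dose per administration at the same frequency is flagged as an increase

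*SAP*

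**What the plan says.** Section 4.1.4 of the SAP treats a concomitant medication as new if it was absent at baseline or if its dosage rose from baseline, and sends the reader to Attachment 9 for the second part. Section 4.10 lists four intervention categories in new/increased form, for example "New/increased bronchodilator/nebulizer treatment". Section 4.10.1 takes its definition of a new intervention from Section 4.1.4.

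Attachment 9 then sets four rules for a drug taken in the same form at both timepoints:

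- **Listed frequencies** (once weekly, daily, monthly, per year and so on): compare doses obtained by "multiplying the dosage per administration with the number of administrations per day or per week, as applicable for both timepoints and compared".
- **Baseline 'other':** "any change to one of the above frequencies will be considered an increase, given that the form remains the same".
- **Baseline PRN or 'occasional':** "any change to another frequency or dose will be considered as an increase".
- **Exception:** a change from PRN "to ‘occasional’ or ‘other’ will not be considered as an increase".

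**The concern.** The attachment exists to detect a rise in dose. Its general rule has a direction, but the PRN/'occasional' rule has none: it asks only whether dose or frequency differs. A halved dose per administration at the same PRN frequency therefore gets the same flag as a doubled one. The 'other' rule has a related gap, because it takes no account of dose and the listed frequencies include sparse ones such as 'Per Year' and 'Every three months'.

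The flag enters several reported results:

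- the table of new medications linked to RSV-confirmed ARIs (4.1.4);
- the season 1 VE with exact Poisson 95% CI, for any RSV disease and for the three case definitions (4.10.1);
- the corresponding VE for seasons 2, 3, 2 and 3 together, and all three (5.9.1);
- the placebo-arm odds ratios relating case definitions to intervention use (4.10.2, 5.11).

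Applying the same rule in both arms does not by itself prevent bias. RSV cases wrongly flagged as treated pull this VE toward the VE against any RSV ARI whenever the truly treated fraction differs between arms.

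**Working it through.** **Step 1: reproduce the SAP's own example.** Attachment 9 gives a nasal corticosteroid at 50 ug once weekly at baseline and 50 ug daily during the ARI. Dose per administration × administrations per week: 50 × 1 = 50 ug per week at baseline and 50 × 7 = 350 ug per week during the ARI. Since 350 > 50, this is an increase, as the SAP says. The second example (guaifenesin 600 mg PRN to 1200 mg once) is also an increase, but the stated reason is the change of frequency, not the higher dose.

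**Step 2: apply the rules as written to test cases.** The doses below are illustrative.

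| Baseline | During ARI | Result under Attachment 9 |
|---|---|---|
| 600 mg daily | 300 mg daily | not an increase (control) |
| 600 mg PRN | 300 mg PRN | increase |
| 600 mg 'occasional' | 300 mg 'occasional' | increase |
| 600 mg PRN | 300 mg once | increase |
| 600 mg 'other' | 300 mg per year | increase |
| 600 mg PRN | 600 mg 'occasional' | not an increase (exception) |
| 600 mg PRN | 1200 mg 'other' | not an increase (exception) |
| 600 mg 'other' | 300 mg or 1200 mg 'other' | no rule stated |

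Rows 2 and 3 are the clear conflict with Section 4.1.4: frequency is unchanged and the only recorded change is a lower dose. Row 5 shows the 'other' rule working without regard to dose. Row 7 shows that the paragraph can also err the other way.

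**Step 3: what it could do to VE.** The SAP gives no count of affected records, so this is illustration only. Assume 70% VE against any RSV ARI (relative risk 0.30), and that p_p = 50% of placebo and p_v = 30% of vaccine RSV cases truly have a new or increased treatment. Let f be the fraction of the remaining cases that are falsely flagged:

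VE = 1 − 0.30 × [p_v + f(1 − p_v)] / [p_p + f(1 − p_p)]

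| f | Calculation | VE |
|---|---|---|
| 0 | 1 − 0.30 × 0.300/0.500 | 82.0% |
| 1% | 1 − 0.30 × 0.307/0.505 | 81.8% |
| 2% | 1 − 0.30 × 0.314/0.510 | 81.5% |
| 10% | 1 − 0.30 × 0.370/0.550 | 79.8% |
| 20% | 1 − 0.30 × 0.440/0.600 | 78.0% |

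If p_v = p_p the ratio is 1 and VE stays at 70% for every f. The shift therefore needs both a non-trivial f and a difference between arms in the treated fraction.

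**The case against.** The best defence is that the general rule cannot be applied here. For PRN or 'occasional' use the number of administrations is unknown, so total intake cannot be calculated at either timepoint and some convention is unavoidable. A participant whose PRN record goes from 600 mg to 300 mg may be taking it more often while ill, and Section 4.10 displays only drugs linked to an ARI or its complication.

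This defends the convention for frequency changes: counting a move from PRN to scheduled dosing as an increase is reasonable. It does not defend the dose-only case. There the recorded evidence points downward, and the rule still returns an increase against the definition in Section 4.1.4.

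The objection on size also stands. A false flag that changes a participant's status needs all of the following:

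- the same drug and form at baseline;
- a PRN, 'occasional' or 'other' baseline record;
- a changed record linked to the ARI;
- a true reduction;
- no other new or increased intervention in that participant.

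This is not one of the three primary endpoints and cannot affect proof of concept. In the illustration the shift lowers VE.

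A reader might infer more than the SAP supports:

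- *That any change from PRN, 'occasional' or 'other' counts.* PRN to 'occasional' or 'other' is expressly excluded, and for 'other' only a move to a listed frequency counts.
- *That every-few-hours schedules are recorded as 'other', so stepping down to daily use is scored as an increase.* Attachment 9 lists the frequencies to which the multiplication applies. It does not say what 'other' contains.
- *That bronchodilators are mostly PRN and so especially affected.* The SAP gives no such figure.

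**Conclusion.** The concern holds in a limited form. As written, Attachment 9 scores a lower dose per administration at unchanged PRN or 'occasional' frequency as an increase, contrary to Section 4.1.4. It scores a move from 'other' to any listed frequency as an increase whatever the dose, and has no rule for a dose-only change within 'other'. This rests on the literal wording alone.

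The effect on the reported VE and odds ratios is unknown, because the number of affected records is not given. It is probably small: in the illustration 1% to 2% false flags move VE by 0.2 to 0.5 percentage points. The 10% and 20% rows move it by 2.2 and 4.0 points, but a reader should not take them as expected, since nothing in the SAP supports rates that high. No size is given for the odds ratios. They would move toward 1 only if false flags were unrelated to case-definition status, which is also an assumption.

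**What to change.** Amend Attachment 9 as follows:

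1. Where the frequency stays PRN, stays 'occasional' or stays 'other', count an increase only if dose per administration is higher than at baseline. This removes the conflict with Section 4.1.4 and fills the gap for 'other'.
2. In the main analysis, keep the convention that PRN, 'occasional' or 'other' to a listed frequency is an increase. Reversing it whenever dose per administration is lower would create the opposite error: 1200 mg PRN to 600 mg four times daily is 2400 mg per day of scheduled treatment, against an unknown PRN intake.
3. Add one sensitivity analysis of the therapeutic-intervention VE that does not count such moves when dose per administration is lower than at baseline.

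The cost is a few lines of wording and derivation code, plus one timing issue. The new-medication definition dates from Amendment 1 (1 April 2020), and Section 1.6 of the current SAP refers to the season 1 primary analysis in the past tense. The season 1 results under the revised flag should therefore be shown as a labelled re-analysis beside those already produced, so that the seasons stay comparable.

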**Attachment 10: Clinically Relevant Complication AE terms**

Asthma & COPD & bronchial hyperreactivity (Preferred terms)
Acute post asthmatic amyotrophy
Asthma late onset
Obstructive airways disorder
Airway remodelling
Asthma
Bronchospasm
Aspirin-exacerbated respiratory disease
Asthma exercise induced
Status asthmaticus
Asthma-chronic obstructive pulmonary disease overlap syndrome
Asthmatic crisis
Wheezing
Bronchial oedema
Bronchial hyperreactivity
Bronchial obstruction
Bronchostenosis
Obliterative bronchiolitis
Bronchiolitis obliterans syndrome
Bronchitis chronic
Bronchospasm paradoxical
Childhood asthma
Chronic obstructive pulmonary disease
Cough variant asthma
Cystic fibrosis
Cystic fibrosis lung
Infective pulmonary exacerbation of cystic fibrosis
Infective exacerbation of chronic obstructive airways disease
Malignant airway obstruction
Occupational asthma
Reactive airways dysfunction syndrome
Reversible airways obstruction
Severe asthma with fungal sensitisation
Unilateral bronchospasm

Respiratory Distress (Preferred Terms)
Respiratory Distress

Bronchitis (Preferred Terms)
Bronchitis
Bronchitis bacterial
Tracheobronchitis
Bronchitis viral
Allergic bronchitis
Asthma
Pertussis
Bronchitis chemical
Bronchitis chronic
Bronchitis fungal
Bronchitis haemophilus
Bronchitis moraxella
Bronchitis mycoplasmal
Bronchitis pneumococcal
Coxsackie bronchitis
Fibrinous bronchitis
Enterobacter tracheobronchitis
Eosinophilic bronchitis

Bronchitis (Preferred Terms)
Herpes simplex bronchitis
Immune-mediated lung disease
Tracheobronchitis mycoplasmal
Noninfective bronchitis
Obstructive airways disorder
Parainfluenzae viral bronchitis
Parainfluenzae viral laryngotracheobronchitis
Pseudomonas bronchitis
Respiratory syncytial virus bronchitis
Sinobronchitis
Streptococcal bronchitis
Tracheobronchitis bacterial
Tracheobronchitis viral

CHF Exacerbation (Preferred Term)
Cardiac failure congestive

Cardiac Arrhythmia (Preferred Terms)
Chronotropic incompetence
Electrocardiogram repolarisation abnormality
Electrocardiogram RR interval prolonged
Electrocardiogram U wave inversion
Electrocardiogram U wave present
Electrocardiogram U-wave abnormality
Sudden cardiac death
Bezold-Jarisch reflex
Bradycardia
Cardiac arrest
Cardiac death
Cardiac telemetry abnormal
Cardio-respiratory arrest
Central bradycardia
Electrocardiogram abnormal
Electrocardiogram ambulatory abnormal
Electrocardiogram change
Heart rate abnormal
Heart rate decreased
Heart rate increased
Loss of consciousness
Palpitations
Rebound tachycardia
Respiratory sinus arrhythmia magnitude abnormal
Respiratory sinus arrhythmia magnitude decreased
Respiratory sinus arrhythmia magnitude increased
Sudden death
Syncope
Tachycardia
Tachycardia paroxysmal
Bradyarrhythmia
Ventricular asystole
Accessory cardiac pathway
Adams-Stokes syndrome
Agonal rhythm
Atrial conduction time prolongation
Atrioventricular block
Atrioventricular block complete

Cardiac Arrhythmia (Preferred Terms)
Atrioventricular block first degree
Atrioventricular block second degree
Atrioventricular conduction time shortened
Atrioventricular dissociation
Atrioventricular node dysfunction
Bifascicular block
BRASH syndrome
Brugada syndrome
Bundle branch block
Bundle branch block bilateral
Bundle branch block left
Bundle branch block right
Conduction disorder
Defect conduction intraventricular
Electrocardiogram delta waves abnormal
Electrocardiogram PR prolongation
Electrocardiogram PR shortened
Electrocardiogram QRS complex prolonged
Electrocardiogram QT prolonged
Electrocardiogram repolarisation abnormality
Lenegre's disease
Long QT syndrome
Paroxysmal atrioventricular block
Sinoatrial block
Trifascicular block
Ventricular dyssynchrony
Wolff-Parkinson-White syndrome
Nodal arrhythmia
Nodal rhythm
Sinus arrest
Sinus arrhythmia
Sinus bradycardia
Sinus node dysfunction
Wandering pacemaker
Arrhythmia
Heart alternation
Heart rate irregular
Holiday heart syndrome
Pacemaker generated arrhythmia
Pacemaker syndrome
Paroxysmal arrhythmia
Pulseless electrical activity
Reperfusion arrhythmia
Withdrawal arrhythmia
Arrhythmia supraventricular
Atrial fibrillation
Atrial flutter
Atrial parasystole
Atrial tachycardia
Congenital supraventricular tachycardia
Frederick's syndrome
Junctional ectopic tachycardia
Sinus tachycardia
Supraventricular extrasystoles
Supraventricular tachyarrhythmia
Supraventricular tachycardia

Cardiac Arrhythmia (Preferred Terms)
ECG P wave inverted
Electrocardiogram P wave abnormal
Retrograde p-waves
Anomalous atrioventricular excitation
Cardiac fibrillation
Cardiac flutter
Extrasystoles
Tachyarrhythmia
Accelerated idioventricular rhythm
Cardiac fibrillation
Parasystole
Rhythm idioventricular
Torsade de pointes
Ventricular arrhythmia
Ventricular extrasystoles
Ventricular fibrillation
Ventricular flutter
Ventricular parasystole
Ventricular pre-excitation
Ventricular tachyarrhythmia
Ventricular tachycardia
Andersen-Tawil syndrome
Arrhythmia neonatal
Arrhythmogenic right ventricular dysplasia
Atrioventricular node dispersion
Brugada syndrome
Foetal arrhythmia
Foetal heart rate disorder
Foetal tachyarrhythmia
Heart block congenital
Junctional ectopic tachycardia
Long QT syndrome congenital
Lown-Ganong-Levine syndrome
Neonatal bradyarrhythmia
Neonatal tachyarrhythmia
Wolff-Parkinson-White syndrome congenital
Baseline foetal heart rate variability disorder
Bradycardia foetal
Bradycardia neonatal
Cardiac arrest neonatal
Cardio-respiratory arrest neonatal
Foetal cardiac arrest
Foetal heart rate acceleration abnormality
Foetal heart rate deceleration abnormality
Neonatal sinus bradycardia
Neonatal sinus tachycardia
Neonatal tachycardia
Nonreassuring foetal heart rate pattern
Tachycardia foetal

Renal Impairment (Preferred Terms)
Acute kidney injury
Atypical haemolytic uraemic syndrome
Oliguria
Anuria

Renal failure
Cardiorenal syndrome
Chronic kidney disease
End stage renal disease
Renal impairment
Crush syndrome
Diabetic end stage renal disease
Hepatorenal failure
Foetal renal impairment
Prerenal failure
Haemolytic uraemic syndrome
Hepatorenal syndrome
Nail-patella syndrome
Renal injury
Neonatal anuria
Pancreatorenal syndrome
Postoperative renal failure
Postrenal failure
Propofol infusion syndrome
Renal failure neonatal
Renal impairment neonatal
Scleroderma renal crisis
Subacute kidney injury
Traumatic anuria

**X-ray or Radiologic Pneumonia (Preferred Terms)**

Angiolymphoid hyperplasia with eosinophilia
Charcot-Leyden crystals
Confirmed e-cigarette or vaping product use associated lung injury
Eosinophilia myalgia syndrome
Eosinophilic bronchitis
Eosinophilic granulomatosis with polyangiitis
Eosinophilic pleural effusion
Eosinophilic pneumonia
Eosinophilic pneumonia acute
Eosinophilic pneumonia chronic
Hypereosinophilic syndrome
Loeffler's syndrome
Pneumonitis
Pneumonitis chemical
Probable e-cigarette or vaping product use associated lung injury
Pulmonary eosinophilia
Pulmonary vasculitis
Eosinophil count abnormal
Eosinophil count increased
Eosinophil percentage abnormal
Eosinophil percentage increased
Eosinophilia
Acute lung injury
Acute respiratory distress syndrome
Airway remodelling
Allergic bronchitis
Allergic cough
Allergic respiratory disease
Allergic respiratory symptom
Alveolar lung disease
Alveolar proteinosis

X-ray or Radiologic Pneumonia (Preferred Terms)
Alveolitis
Aspirin-exacerbated respiratory disease
Asthma
Asthma late onset
Asthma-chronic obstructive pulmonary disease overlap syndrome
Asthmatic crisis
Atopic cough
Autoimmune lung disease
Bronchial hyperreactivity
Bronchial obstruction
Bronchiolitis
Bronchiolitis obliterans syndrome
Bronchospasm
Childhood asthma
Complications of transplanted lung
Cough variant asthma
Cystic lung disease
Diffuse alveolar damage
Diffuse panbronchiolitis
Drug reaction with eosinophilia and systemic symptoms
Forced expiratory flow decreased
Forced expiratory volume abnormal
Forced expiratory volume decreased
Fractional exhaled nitric oxide abnormal
Fractional exhaled nitric oxide increased
Functional residual capacity abnormal
Functional residual capacity increased
Goodpasture's syndrome
Granulomatosis with polyangiitis
Hypersensitivity pneumonitis
Hyperventilation
Hypocapnia
Hypoxia
Idiopathic interstitial pneumonia
Immune-mediated lung disease
Interstitial lung disease
Lung hyperinflation
Lung infiltration
Lung opacity
Lung transplant rejection
Lupus pneumonitis
Lymphangioliomyomatosis
Myalgia
Obliterative bronchiolitis
Obstructive airways disorder
Occupational asthma
Organising pneumonia
PCO2 abnormal
PCO2 decreased
Peak expiratory flow rate abnormal
Peak expiratory flow rate decreased
Pneumonia
PO2 abnormal
PO2 decreased
Polyarteritis nodosa
Prolonged expiration

X-ray or Radiologic Pneumonia (Preferred Terms)
Pulmonary granuloma
Pulmonary radiation injury
Pulmonary sensitisation
Pulmonary toxicity
Radiation alveolitis
Radiation pneumonitis
Respiratory alkalosis
Reversible airways obstruction
Rheumatoid lung
Small airways disease
Status asthmaticus
Tachypnoea
Toxic oil syndrome
Transfusion-related acute lung injury
Wheezing
Actinomycotic pulmonary infection
Acute pulmonary histoplasmosis
Atypical mycobacterial pneumonia
Atypical pneumonia
Blastomycosis
Bronchopulmonary aspergillosis
Burkholderia cepacia complex infection
Burkholderia pseudomallei infection
Candida pneumonia
Chlamydial infection
Chronic pulmonary histoplasmosis
Coccidioidomycosis
COVID-19 pneumonia
Embolic pneumonia
Enterobacter pneumonia
Haemophilus infection
Haemorrhagic pneumonia
Hantavirus pulmonary infection
Herpes simplex pneumonia
Histoplasmosis
Infectious pleural effusion
Lung abscess
Metapneumovirus pneumonia
Miliary pneumonia
Paraneoplastic pneumonia
Parasitic pneumonia
Pleural infection
Pleural infection bacterial
Pleurisy viral
Pneumocystis jirovecii pneumonia
Pneumonia
Pneumonia acinetobacter
Pneumonia adenoviral
Pneumonia anthrax
Pneumonia bacterial
Pneumonia blastomyces
Pneumonia bordetella
Pneumonia chlamydial
Pneumonia cryptococcal
Pneumonia cytomegaloviral
Pneumonia escherichia

X-ray or Radiologic Pneumonia (Preferred Terms)
Pneumonia fungal
Pneumonia haemophilus
Pneumonia helminthic
Pneumonia herpes viral
Pneumonia influenzal
Pneumonia klebsiella
Pneumonia legionella
Pneumonia measles
Pneumonia moraxella
Pneumonia mycoplasmal
Pneumonia necrotising
Pneumonia parainfluenzae viral
Pneumonia pneumococcal
Pneumonia proteus
Pneumonia pseudomonal
Pneumonia respiratory syncytial viral
Pneumonia salmonella
Pneumonia serratia
Pneumonia staphylococcal
Pneumonia streptococcal
Pneumonia toxoplasmal
Pneumonia tularaemia
Pneumonia viral
Pneumonic plague
Post procedural pneumonia
Pulmonary echinococcosis
Pulmonary mucormycosis
Pulmonary nocardiosis
Pulmonary paracoccidioidomycosis
Pulmonary sepsis
Pulmonary sporotrichosis
Pulmonary syphilis
Pulmonary trichosporonosis
Pulmonary tuberculosis
Pyopneumothorax
Septic pulmonary embolism
Tuberculosis
Tuberculous pleurisy
Varicella zoster pneumonia
Acinetobacter infection
Acinetobacter test positive
Adenovirus infection
Adenovirus test positive
Aspergillus infection
Aspergillus test positive
Aspiration tracheal abnormal
Atelectasis
Atypical mycobacterial infection
Atypical mycobacterial lower respiratory tract infection
Auscultation
Avian influenza
Bacterial test positive
Bronchopneumopathy
Burkholderia test positive
Carbon dioxide abnormal
Carbon dioxide increased

X-ray or Radiologic Pneumonia (Preferred Terms)
Chest X-ray abnormal
Chlamydia test positive
Coronavirus infection
Coronavirus test positive
COVID-19
Coxiella test positive
Creptitations
Cryptococcosis
Culture throat positive
Disseminated aspergillosis
Disseminated blastomycosis
Disseminated coccidioidomycosis
Disseminated mucormycosis
Disseminated paracoccidioidomycosis
Disseminated sporotrichosis
Disseminated tuberculosis
Egobronchophony
Empyema
Enterobacter infection
Enterobacter test positive
Escherichia infection
Escherichia test positive
Francisella test positive
Fungal test positive
H1N1 influenza
H2N2 influenza
H3N2 influenza
Haemophilus test positive
Haemoptysis
Hantavirus test positive
Human metapneumovirus test positive
Hypoventilation
Hypoxia
Increased bronchial secretion
Influenza
Influenza A virus test positive
Influenza virus test positive
Klebsiella infection
Klebsiella test positive
Legionella infection
Legionella test positive
Lower respiratory tract congestion
Lower respiratory tract herpes infection
Lower respiratory tract infection
Lower respiratory tract infection bacterial
Lower respiratory tract infection fungal
Lower respiratory tract infection viral
Lung consolidation
Lung infiltration
Lung opacity
MERS-CoV test positive
Metapneumovirus infection
Middle East respiratory syndrome
Moraxella infection
Moraxella test positive
Mucormycosis

X-ray or Radiologic Pneumonia (Preferred Terms)
Mycobacterial infection
Mycobacterium test positive
Mycoplasma infection
Mycoplasma test positive
Nocardiosis
Organising pneumonia
Oxygen saturation abnormal
Oxygen saturation decreased
Paracoccidioides infection
PCO2 abnormal
PCO2 decreased
Percussion test abnormal
Pleural effusion
Pleural rub
Pleuritic pain
Pneumococcal bacteraemia
Pneumococcal infection
Pneumococcal sepsis
Pneumocystis test positive
Pneumovirus test positive
PO2 abnormal
PO2 decreased
Productive cough
Proteus infection
Proteus test positive
Pseudomonas infection
Pseudomonas test positive
Psittacosis
Pulmonary congestion
Pulmonary imaging procedure abnormal
Pulmonary tuberculoma
Q fever
Rales
Respiratory tract infection
Respiratory tract infection bacterial
Respiratory tract infection fungal
Respiratory tract infection viral
Rhonchi
SARS-CoV-1 test positive
SARS-CoV-2 antibody test positive
SARS-CoV-2 test false negative
SARS-CoV-2 test positive
Serratia infection
Serratia test positive
Severe acute respiratory syndrome
Sporotrichosis
Sputum abnormal
Sputum culture positive
Sputum discoloured
Sputum purulent
Staphylococcal infection
Staphylococcus test positive
Streptococcal infection
Streptococcus test positive
Suspected COVID-19
Tachypnoea

X-ray or Radiologic Pneumonia (Preferred Terms)
Tularaemia
Use of accessory respiratory muscles
Venous oxygen saturation abnormal
Venous oxygen saturation decreased

Respiratory Arrest or Failure (Preferred Terms)
Acute respiratory distress syndrome
Acute respiratory failure
Agonal respiration
Apnoea
Apnoeic attack
Bradypnoea
Breath holding
Breath sounds abnormal
Breath sounds absent
Cardio-respiratory distress
Central-alveolar hypoventilation
Chronic respiratory failure
Hypopnoea
Hypoventilation
Hypoventilation neonatal
Infantile apnoea
Lung hypoinflation
Meconium aspiration syndrome
Neonatal respiratory arrest
Neonatal respiratory depression
Neonatal respiratory distress
Neonatal respiratory distress syndrome
Neonatal respiratory failure
Postoperative respiratory distress
Postoperative respiratory failure
Respiratory arrest
Respiratory depression
Respiratory depth decreased
Respiratory distress
Respiratory failure
Respiratory paralysis
Respiratory rate decreased
Adaptive servo-ventilation
Alveolar oxygen partial pressure abnormal
Alveolar oxygen partial pressure decreased
Alveolar-arterial oxygen gradient increased
Anoxia
Asphyxia
Automatic positive airway pressure
Bilevel positive airway pressure
Blood gases abnormal
Blood pH abnormal
Blood pH decreased
Capnogram abnormal
Carbon dioxide abnormal
Carbon dioxide increased
Cardiac arrest
Cardiac arrest neonatal
Cardiopulmonary failure
Cardio-respiratory arrest

Respiratory Arrest or Failure (Preferred Terms)
Cardio-respiratory arrest neonatal
Cheyne-Stokes respiration
Chronic respiratory disease
Clubbing
Continuous positive airway pressure
Cyanosis central
Death neonatal
Dependence on oxygen therapy
Dependence on respirator
Diaphragmatic pacemaker insertion
Dyspnoea at rest
Endotracheal intubation
End-tidal CO2 abnormal
End-tidal CO2 decreased
Hyperbaric oxygen therapy
Hypercapnia
Hypercapnic coma
Hypoxia
Intermittent positive pressure breathing
Irregular breathing
Life support
Lung assist device therapy
Mechanical ventilation
Mechanical ventilation complication
Neonatal anoxia
Neonatal asphyxia
Neonatal hypoxia
Neonatal respiratory acidosis
Neonatal respiratory distress syndrome prophylaxis
Neonatal tachypnoea
Orthopnoea
Oxygen saturation abnormal
Oxygen saturation decreased
Oxygen saturation immeasurable
Oxygen therapy
PaO2/FiO2 ratio decreased
PCO2 abnormal
PCO2 decreased
PCO2 increased
PO2 abnormal
PO2 decreased
Positive end-expiratory pressure
Positive expiratory pressure therapy
Respiration abnormal
Respiratory acidosis
Respiratory disorder
Respiratory disorder neonatal
Respiratory fatigue
Respiratory fume inhalation disorder
Respiratory gas exchange disorder
Respiratory therapy
Tachypnoea
Transient tachypnoea of the newborn
Use of accessory respiratory muscles
Venous oxygen partial pressure abnormal
Venous oxygen partial pressure decreased

Respiratory Arrest or Failure (Preferred Terms)
Venous oxygen saturation abnormal
Venous oxygen saturation decreased
Ventilation perfusion mismatch
Ventilation/perfusion scan abnormal
Wean from ventilator
Weaning failure
Xyphoid retraction
Acute respiratory failure
Agonal respiration
Apnoea
Apnoeic attack
Bradypnoea
Breath holding
Breath sounds abnormal
Breath sounds absent
Central-alveolar hypoventilation
Hypopnoea
Hypoventilation
Hypoventilation neonatal
Infantile apnoea
Lung hypoinflation
Neonatal respiratory arrest
Neonatal respiratory depression
Neonatal respiratory failure
Postoperative respiratory failure
Respiratory arrest
Respiratory depression
Respiratory depth decreased
Respiratory failure
Respiratory paralysis
Respiratory rate decreased
Adaptive servo-ventilation
Alveolar oxygen partial pressure abnormal
Alveolar oxygen partial pressure decreased
Anoxia
Apnoea test abnormal
Asphyxia
Automatic positive airway pressure
Bilevel positive airway pressure
Blood gases abnormal
Blood pH abnormal
Blood pH decreased
Capnogram abnormal
Carbon dioxide abnormal
Carbon dioxide increased
Cardiac arrest
Cardiac arrest neonatal
Cardiopulmonary failure
Cardio-respiratory arrest
Cardio-respiratory arrest neonatal
Cardio-respiratory distress
Cheyne-Stokes respiration
Continuous positive airway pressure
Cyanosis
Cyanosis central
Death neonatal

Respiratory Arrest or Failure (Preferred Terms)
Dependence on oxygen therapy
Dependence on respirator
Diaphragmatic pacemaker insertion
Dyspnoea
End-tidal CO2 abnormal
End-tidal CO2 decreased
Hyperbaric oxygen therapy
Hypercapnia
Hypercapnic coma
Hypoxia
Intermittent positive pressure breathing
Irregular breathing
Life support
Lung assist device therapy
Mechanical ventilation
Mechanical ventilation complication
Neonatal anoxia
Neonatal asphyxia
Neonatal dyspnoea
Neonatal hypoxia
Neonatal respiratory acidosis
Neonatal respiratory distress syndrome prophylaxis
Oxygen saturation abnormal
Oxygen saturation decreased
Oxygen saturation immeasurable
Oxygen therapy
PaO2/FiO2 ratio decreased
PCO2 abnormal
PCO2 increased
PO2 abnormal
PO2 decreased
Positive end-expiratory pressure
Respiration abnormal
Respiratory acidosis
Respiratory disorder
Respiratory disorder neonatal
Respiratory distress
Respiratory fume inhalation disorder
Respiratory gas exchange disorder
Respiratory therapy
Sleep apnoea syndrome
Venous oxygen partial pressure abnormal
Venous oxygen partial pressure decreased
Venous oxygen saturation abnormal
Venous oxygen saturation decreased
Ventilation perfusion mismatch
Ventilation/perfusion scan abnormal
Wean from ventilator
Weaning failure

Pulmonary Embolism (Preferred Terms)
Pulmonary embolism
Anaphylactoid syndrome of pregnancy
Cement embolism
Pulmonary infarction

Metastatic pulmonary embolism
Obstetrical pulmonary embolism
Post procedural pulmonary embolism
Pulmonary artery thrombosis
Pulmonary microemboli
Pulmonary oil microembolism
Pulmonary thrombosis
Pulmonary tumour thrombotic microangiopathy
Pulmonary venous thrombosis
Septic pulmonary embolism

